3.3.3.3. Autologous Transfer

The stylette from the Touhy needle described above will be removed. Negative aspiration will confirm that the needle has not pierced the dura or vasculature. Using sterile technique, the autologous blood sample will be slowly injected into the epidural space through the Touhy needle. Following epidural needle removal, pressure dressings will be applied to achieve hemostasis. The patient will be returned to the supine position and will remain in this position for one hour.

3.3.4. SPG block

Immediately after obtaining informed consent, inclusion in the study, transport to the OR holding suite, randomization to the treatment arm of this study, completion of the time-out procedure and initial symptom assessment, the patient will receive an SPG block. Vital-sign monitoring of the patient as described above will commence once the patient is checked into this area.

The subject will be placed in the supine position with the neck extended to the extent that he or she can tolerate with the use of a shoulder roll and head-of-the-bed positioning as appropriate. One cm of 5% lidocaine ointment will be applied to the end of each of two sterile 6-inch hollow-plastic-shaft cotton-tip applicator (Cardinal Health, Dublin, Ohio). One so-treated applicator will be inserted each of the patient's two both nares, posteriorly directed toward the anatomic location of

the sphenopalatine ganglion. Correct positioning will evidenced by slight resistance at the appropriate depth. Four mL of 1% lidocaine solution will then be slowly injected into the hollow shaft of the applicator and allowed to anesthetize the ganglion topically by gravity flow for 30 minutes. The applicators will be removed from the nares and the subject will be returned to the supine position with a neutral neck position.

Symptom assessment, determination of treatment failure, and performance subsequent procedures will be as described in section 3.2.3. In addition, the investigator will assess whether the patient has any adverse effects of this procedure. These are rare, but could include pain in the nares, epistaxis, pharyngeal numbness and a bitter taste in the mouth.

3.4. Duration of Study

The study will last 8 years in duration.

3.5. Study Sites

This is a single-site clinical research study that will be conducted at Robert Wood Johnson University Hospital, New Brunswick, NJ 08901 by the PI and SIs of Rutgers Robert Wood Johnson Medical School, part of Rutgers, the State University of New Jersey.

3.6. Sample Size Justification

We derive data for calculation of the sample size from the prior studies noted above. In the control group (Table 7, Group 1, EBP) we predict a success rate of 84% as noted by van Kooten et al. (7). In the treatment group (Table 7, group 2, SPG block) we predict a success rate of 68% based on our pilot study (15). If therefore there is a true 16% (84% - 68%) in favor of the EBP group then 210 subjects are required to be 90% certain that the upper limit of a one-sided 95% confidence interval will exclude a difference in favor of the EBP group of more than 33%. This calculation was performed using the formula below (Table 9 and Equation) using an online calculator <https://www.sealedenvelope.com/power/binary-noninferior/>).

Our chosen non-inferiority limit d of 33% means that we believed saving 67% (100% – 33%) of patients from the invasive EBP in favor of the non-invasive, cost-effective SPG block would be clinically relevant.

Table 9. Values used for determination of sample size

Variable	Description	Value
n	sample size	210
ϕ^{-1}	cumulative distribution function of a standardized normal deviate	n/a
α	significance level, alpha	0.05
β	false negative rate, beta, where power $(1 - \beta) = 0.90$	0.10
π_s	success rate in control group	0.84
π_e	success rate in treatment group	0.68
d	non-inferiority limit	0.33

Equation. Sample size calculation for a binary outcome non-inferiority trial

$$n = \left(\phi^{-1}(\alpha) + \phi^{-1}(\beta) \right)^2 \times \frac{\pi_s \times (100 - \pi_s) + \pi_e \times (100 - \pi_e)}{\pi_s - \pi_e - d^2}$$

4. Study Variables

4.1. Independent Variables and Interventions

As described in Section 3.3 “Procedures”, above, the two interventions to be studied are the EBP and the SPG block. Though the EBP is the standard of care for definitive treatment for PDPH, both procedures are well documented in the literature. Furthermore, the SPG block has already been shown in our pilot study to decrease the symptom severity in patients with PDPH, thus patients in both arms of this study will receive a treatment modality.

4.1.1. Drug and device Intervention for EBP

The procedure for the EBP is described in Section 3.3.3 above. All of the drugs and equipment required are either part of the kit noted or readily available in the Regional Nerve Block area. No equipment or drug described is experimental or investigational. The Current Procedural Terminology (CPT®, American Medical Association, Chicago, Illinois) code for EBP is 62273, “Injection, epidural, of blood or clot patch”.

4.1.2. Drug and device Intervention for SPG block

The procedure for the SPG block is described in Section 3.3.4 above. All of the drugs and equipment required are readily available in the Regional Nerve Block area. No equipment or drug described is experimental or investigational. Though a CPT code exists for a SPG block involving an injection (64505), as the technique described herein is non-invasive and does not involve injection, and as a specific code does not exist for this technique, it will be included in the

appropriate level Evaluation and Management (E/M) code. (AMA Knowledgebase #5436).

4.2. Dependent Variables and Outcome Measures

Symptom assessment as described in section 3.2.3 will be by personal or telephone interview by the PI or SI using a questionnaire (Attachment 1). The laboratory tests noted in the exclusion criteria including the pregnancy test and platelet count (Table 6), and the medical history interview are not specific to this study, and would be part of standard practice if the patient sought intervention for a PDPH outside of this study. No specimens will be taken.

4.3. Risk of Harm

As noted earlier, both the EBP and the SPG block are well-established procedures with favorable safety profiles. The limited risks of the procedures themselves are listed in the procedure sections above, but these are not specific to inclusion in this study.

Subjects who are enrolled in this study will be randomized to either one of the treatment arms whereas patients would otherwise be given the choice of which one they prefer. There is a risk of psychological or emotional harm that is intrinsic to any such randomized treatment study; however, this risk is minimized since as stated earlier, all subjects retain the ability to be excluded from the study and undergo the procedure of their choice at any point in the study process.

This study aims to determine whether there is a difference in the symptom-free period. If the study ultimately finds that one treatment maintains a longer symptom-free period, the subject in the other arm of the study could face having to undergo a repeated or new procedure. Again, this harm is minimal, since symptom-assessment scheme is such that in the period that symptoms are likely to relapse after a failed treatment (1–24 hours), the patient will be repeatedly assessed.

The subject may encounter minor inconvenience after receiving two follow-up phone calls for symptom assessment instead of the standard one call. This would account for approximately 5 minutes of extra time out of the patient's day.

4.4. Potential for Benefit

All patients enrolled in this study will receive one type of treatment for a PDPH. Since we seek to enroll all patients who meet the minimum criteria for the diagnosis of PDPH (Table 2), all included subjects will potentially be spared pain medications that are often given during conservative treatment efforts as well as avoiding having to cope with these symptoms while medical management is attempted.

If one arm treatment is found to be better than the other, the subjects in that group may experience a quicker relief of symptoms, and improvement in the overall quality of life.

Following the conclusion of the study, the medical community will gain knowledge about the best method by which certain individuals may be treated for PDPH.

5. Data Handling and Statistical Analysis

5.1. Safeguarding Data

All data will be stored in a locked file in the office of the principal investigator with limited access. Once the subject is enrolled, he or she will be assigned a number that will both assign the subject to one of the arms as well as serve as the identification number for the storage of results. Since this study involves multiple contacts with the subject, one set of data will contain demographic information including the patient's name and telephone number, which is recognized as protected health information (PHI). The other set of data will only reference the assigned number and will contain the symptom assessment data. The link to the protected health information (PHI) will be stored separately from the study files and will be destroyed after all the data has been collected and analyzed. Up to 500 subjects may sign the informed consent for participating in this trial. This number is to ensure 210 subjects complete each study group below. Therefore, we will be replacing subjects that do not complete the study as designed.

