Our recent literature review has suggested that there are multiple techniques for performing the sphenopalatine ganglion block. A proven method for performing the block involves using a cotton tip applicator to place lidocaine gel in the middle posterior pharynx followed by administration of 1 mL of 4% lidocaine solution through the plastic channel of the applicator, all simply by placing the soft, flexible, cotton-tip applicator into the nares (14). This technique of transmucosal application of local anesthetics was proposed by Lebovits et al. (15) and others (16). The side effects associated with SPG blocks are minimal, often limited to the bitter taste of the anesthetic solution. The theoretical rare risks of anaphylaxis and severe epistaxis exist, but have not been described in the literature.

The SPGB has been described in the literature for the treatment of cluster headaches and is recognized as a treatment for this condition when other modalities fail (17-20). A study has investigated its use for the treatment of PDPH (21). Twenty-eight patients with PDPH were offered a SPG block prior to EBP. Nineteen of 28 patients noted relief and only 9 patients eventually needed an epidural blood patch after 1 week. Moreover, most patients (~93%) noted relief of headache at and beyond 72 hours following the procedure significantly decreasing morbidity during the otherwise symptomatic period. In this pilot study, approximately 68% of patients were saved from having to undergo the invasive EBP in favor of a more cost-effective and less invasive technique (21). This study has helped establish the

sphenopalatine ganglion block as a standard of care for the treatment of PDPH, especially when other modalities fail or are not preferred by the patient. The SPGB appears as a treatment in the common physician reference resource UpToDate® (Waltham, MA) for the treatment of adverse effects of neuraxial anesthesia (22).

3. Research Design and Methods

We propose to treat patients suffering from a severe and incapacitating headache resulting from dural puncture. Both the EBP and SPGB therapies have been shown to reduce the intensity of PDPH. The design of this study seeks to determine the duration of relief associated with both therapies and to compare the patient's satisfaction with both techniques.

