3.2. Study Design

3.2.1. Type

This is a non-inferiority trial comparing the SPGB to the EBP for the treatment of PDPH. The study is not blinded to the subject or investigator. Due to the nature of the procedure and the anatomical site of intervention, both will know which method they are receiving or delivering. We acknowledge this as a limitation of our study but reiterate that blinding one or both parties is not feasible.

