3.2.2. Randomization

Subjects suffering from PDPH shall be randomized to one of two groups (**Table 7**) by a random number generation spreadsheet (Excel, Microsoft, Redmond, Washington).

Table 7. Patients with PDPH to be treated for their symptoms are randomized to one of the two groups below

Group	Intervention
1, EBP (control)	EBP as described below
2, SPG block (treatment)	SPG block as described below

[figure not shown]

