5.2. Analysis

Nonparametric data such as those resulting from the VAS assessments from the two groups will be compared using the Mann–Whitney U test. The Student's *t*-test will be used to compare normally distributed continuous variables. A *p* value of less than or equal to 0.05 will be considered statistically significant.

6. Data and Safety Monitoring

All subjects enrolled in this study will receive at least one of two types of treatment for their PDPH. Both the EBP and SPG block are low-risk procedures that can be and are routinely performed in an office setting on outpatients in our pain clinic at the New Jersey Pain Institute. Furthermore, neither of these techniques are experimental; rather, their methods are well documented in literature and are common procedures in the pain medicine field.

Subjects who undergo the procedures within this study will have additional monitoring as opposed to patients who undergo the same procedures outside of this study. Patients in this study will receive two follow-up phone calls to assess their symptoms and to expedite the availability of any additional procedures that need to be performed. These telephone calls will also serve to inform the SIs and PI if the patients are experiencing any undue and unexpected harms as a result of this study. As all of the investigators in this study are in the department of anesthesia, they are the best equipped to identify potential side effects and treatment.

All subjects enrolled in this study will be given a contact sheet including phone numbers by which they may reach the PI, emergency room, the pain clinic, and the Pain Medicine

physician-on-call who, as previously stated, is available continuously by mobile telephone.

7. Reporting Results

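### Section 5.1 targets 210 completers in each group, but the section 3.6 inputs support 210 in total (105 per group at 1:1), so the stated 90% power does not describe the target

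*Combined protocol and SAP*

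**What the plan says.** Section 3.6 (Sample Size Justification) predicts 84% success with the epidural blood patch (EBP) and 68% with the sphenopalatine ganglion block (SPGB), sets a non-inferiority limit of 33 percentage points, and states: "then 210 subjects are required to be 90% certain that the upper limit of a one-sided 95% confidence interval will exclude" a difference larger than that limit. Table 9 lists n = 210 simply as the sample size, with alpha 0.05 and beta 0.10. Neither place says whether 210 is the total or the number per group.

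Section 3.2.2 (Randomization) gives no allocation ratio: "Subjects suffering from PDPH shall be randomized to one of two groups".

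Section 5.1 (Safeguarding Data) is the only place that says what 210 counts. It sets a ceiling, "Up to 500 subjects may sign the informed consent for participating in this trial", and explains it: "This number is to ensure 210 subjects complete each study group below". It adds that subjects who do not complete will be replaced. No dropout rate is given, and nothing derives 210 per group.

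**The concern.** The same number appears with two possible meanings, a factor of two apart. If 210 is the total that the section 3.6 calculation produces, section 5.1 doubles it without explanation, and the 90% power quoted in section 3.6 belongs to a trial half the size of the one being run.

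This is not a loss of power. At stake are about 210 additional completers whom the justification does not call for, in a single-site study planned to last 8 years (sections 3.4 and 3.5). There is also uncertainty about when recruitment is complete. The design is open-label (section 3.2.1: "The study is not blinded to the subject or investigator"), so two readings of the target leave two possible stopping points, 210 or 420, open to people who can see outcomes as they accrue.

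**Working it through.** **Inputs.** From section 3.6 and Table 9: EBP success 0.84; SPGB success 0.68; margin 0.33; one-sided alpha 0.05 (z = 1.645); power 0.90 (z = 1.282). Assumed, because section 3.2.2 states no ratio: 1:1 allocation. The equation printed under Table 9 may have been damaged in text extraction, so the standard formula with unpooled variance is used instead.

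**1. Reproduce the plan's figure.**

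n per group = (1.645 + 1.282)² × (0.84 × 0.16 + 0.68 × 0.32) / (0.33 − 0.16)²
= 8.564 × (0.1344 + 0.2176) / 0.0289
= 8.564 × 0.352 / 0.0289 = 104.3, rounded up to 105.

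Total = 2 × 105 = 210. The stated 210 reproduces exactly as a total and does not reproduce as a per-group number.

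**2. Could other settings give 210 per group?** At 1:1 with the same rates and margin:

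| One-sided alpha | Power | n per group |
|---|---|---|
| 0.05 | 90% | 105 |
| 0.05 | 95% | 132 |
| 0.025 | 90% | 128 |
| 0.025 | 95% | 159 |

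None reaches 210.

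**3. Does the 1:1 assumption drive the result?** With r = SPGB:EBP, n(EBP) = 8.564 × (0.1344 + 0.2176/r) / 0.0289 and n(SPGB) = r × n(EBP), each rounded up:

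| SPGB:EBP | SPGB | EBP | Total |
|---|---|---|---|
| 1:2 | 85 | 169 | 254 |
| 1:1 | 105 | 105 | 210 |
| 1.5:1 | 125 | 83 | 208 |
| 1.6:1 | 129 | 81 | 210 |
| 2:1 | 145 | 73 | 218 |

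A total of 210 does not prove 1:1, since 1.6:1 gives it too. But no ratio from 1:2 to 2:1 needs more than 169 in a group or 254 in total.

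**4. Power at each size.** Power = Φ{[0.33 − (0.84 − p)] / √[(0.1344 + p(1 − p))/n] − 1.645}, where p is the true SPGB rate, n is per group, and EBP stays at 84%.

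- p = 0.68, n = 105: 0.17 / √(0.352/105) − 1.645 = 2.936 − 1.645 = 1.291, so 90.2%.
- p = 0.68, n = 210: 0.17 / √(0.352/210) − 1.645 = 4.152 − 1.645 = 2.507, so 99.4%.

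A simulation of the upper Wald limit (400,000 runs) gave 90.3% and 99.4%.

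**5. How far the surplus depends on the 68%.** That rate comes from a pilot (section 2: "Nineteen of 28 patients noted relief and only 9 patients eventually needed an epidural blood patch after 1 week"). 19/28 = 67.9%, with a 95% Wilson interval of 49.3% to 82.1%. The lower rates below are illustrative and do not come from the protocol.

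| True SPGB rate | Power, 105 per group | Power, 210 per group |
|---|---|---|
| 68% | 90.2% | 99.4% |
| 65% | 77.0% | 95.8% |
| 62% | 58.3% | 83.5% |

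With 210 per group, power is 90% at an SPGB rate of about 63.2%. If the rates are kept, it is 90% at a margin of about 28 points. The protocol states neither value.

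**6. The consent cap.** For 420 completers, 500 consents allow (500 − 420)/500 = 16% loss. For 210 completers they allow (500 − 210)/500 = 58%. The cap fits the per-group reading in section 5.1.

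**The case against.** Five points can be made on the other side.

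- **Section 3.6 never calls 210 a total, and 105 per group rests on an assumed 1:1 split.** True. But section 5.1 sets equal numbers in the two groups, and no ratio from 1:2 to 2:1 needs 210 in either group.
- **A larger sample still meets a 90% requirement, so no power statement is false.** Partly right. Section 5.1 makes no power claim of its own. It remains true that 210 subjects were justified, 420 are sought, and the reader is given a power figure for the smaller number only.
- **The sentence in section 5.1 may be misplaced.** It sits under data safeguarding and points to study groups that are not listed after it in that section. The cap of 500 nevertheless fits it, which makes a simple slip of wording less likely.
- **The cap is a ceiling on consents, some of which may be lost to exclusions before randomisation.** This stands. The 16% and 58% figures mix such exclusions with non-completion, and a cap of 500 does not strictly contradict a total of 210. It would need a justification or a smaller value.
- **The power figures are less firm than they look.** This stands as well. Section 5.2 names only Mann–Whitney and t-tests, no passage defines success for both arms, and the 84% is a one-week rate (section 2) while follow-up ends at 48 hours (section 3.2.3). Both 90.2% and 99.4% are planning figures at the section 3.6 inputs.

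The best defence of the larger number is that 68% rests on only 28 patients. That argument is reasonable, but the protocol does not make it.

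**Conclusion.** The concern holds. At 1:1 allocation the section 3.6 inputs give 105 per group and 210 in total, while section 5.1 sets 210 completers per group and 420 in total. The excess is 105 per arm, or 210 overall, with no reason given. The quoted 90% power belongs to the smaller trial; at the same inputs the section 5.1 target has about 99.4%. The headcount discrepancy does not reduce power and leaves the type I error, the margin and the treatment estimate unaffected. The size of the surplus depends on the assumed SPGB rate: at 62%, even 210 per group would give only about 84% power. The power figures also presuppose a binary non-inferiority comparison, which the analysis section does not yet name. The sample size should be corrected, but the discrepancy does not invalidate the trial.

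**What to change.** Amend the protocol so that n is labelled as per group or total, the allocation ratio is stated in section 3.2.2, and section 3.6, Table 9, section 5.1 and the cap agree. There are two coherent options:

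- **(a)** 105 completers per group, 210 in total, 90% power, with the cap of 500 rescaled or justified.
- **(b)** 210 completers per group, 420 in total, with the reason for the larger size written down and power restated as about 99.4% for the binary comparison at 84% versus 68% and a 33-point margin. If uncertainty in the pilot rate is the reason, the lower SPGB rate being guarded against should be stated.

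Under either option, section 5.2 must name the binary non-inferiority comparison. It now goes no further than "Nonparametric data such as those resulting from the VAS assessments from the two groups will be compared" by rank test, plus a t-test for normally distributed variables, and without the binary comparison neither power figure applies. Naming it is necessary but not sufficient, because the comparison also needs a definition of success.

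Make the choice without reference to accumulating outcome data, and record it with a date. This matters most for option (a), which halves the section 5.1 target in an open-label trial. The margin should not be re-derived to fit the larger sample.

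The cost is one amendment to sections 3.2.2, 3.6 (with Table 9), 5.1 and 5.2. The reconciliation needs no new data collection. Option (a) also needs the dated record, and option (b) the written rationale.

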The EBP has traditionally been the definitive mode of treatment in patients with PDPH. This intervention involves the autologous transfusion of a patient’s blood from a sterile peripheral site into the epidural space. Several studies have established the EBP as standard of care for PDPH. A randomized, controlled clinical trial has showed that EBPs resolve PDPHs after one week in 84% of patients compared to 14% with placebo (7). Another prospective, randomized, double-blinded trial compared EBP to conservative management (fluid replacement, non-steroidal anti-inflammatory drugs, and caffeine) for the treatment of PDPH. (8). These authors found that when treated conservatively patients with PDPH noted little to no change in headache, as reported on a visual analog scale (VAS). Their headaches rated 8.2 ± 1.4 both before and after treatment. In the group who received an EBP, patients reported a decrease in headache from 8.0 ± 1.6 to 0.7 ± 0.16 . The authors further state that “The epidural blood patch represents the first choice treatment of PDPH no matter the etiology, being significantly superior to the conventional treatment which did not affect pain scores” (8). These studies have helped establish the EBP as a standard of care for PDPH. It now appears as a listed treatment for PDPH in common physician reference resources such as UpToDate® (Waltham, MA) (9).

Originally, the EBP was thought to act through a tamponade effect, plugging the dural defect and preventing the further leakage of CSF. As noted above, this is unlikely the true mechanism as patients often report immediate relief, which could not be explained by cessation of the minute flow of CSF. The more contemporary explanation is that the EBP does in fact plug the dural tear, but in doing so, it prevents the equilibration of CSF pressure with the atmospheric pressure. Injection of blood into the epidural space immediately raises

the CSF pressure within the closed spinal canal space and thus causes reflex cerebral vasoconstriction. Consequently, subdural venous collapse is restored and the headache subsides.

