For patients randomized to group 2 (SPGB), the symptoms in Table 8 will be assessed and graded at 30 min post-procedure. If this treatment does not decrease the patient's "orthostatic headache" severity past the pre-treatment score, then the SPGB will be performed for a second time. The symptoms will be graded again 30 min after the second block. If the "orthostatic headache" severity score is still unchanged, then a SPGB will be performed for a third time. If the "orthostatic headache" severity score remains unchanged at the 30 min mark following the third SPGB, the procedure will be considered a failure and conservative measures or an EBP will be offered to the patient.

If the first, second or third SPGB succeeds in decreasing the "orthostatic headache" severity score at 30 min post-procedure, the symptoms in Table 8 will be assessed and graded again at 60 min post-procedure. In all cases, the same symptoms will be assessed at 24 and 48 hours post-procedure in the manner noted above. If patients in any group on telephone interview note dissatisfaction with the alleviation of the symptoms or if the symptoms return, they will be given the option of arriving at the Pain Clinic at the New Jersey Pain Institute during normal clinic hours or to the emergency room (ER) after hours. At that time, they will be given the option of an EBP, SPGB or medical management. This is the same as what would be offered if a patient underwent treatment for a PDPH outside of this study and had symptoms return afterward.

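### Section 5.1 replaces randomised subjects who do not complete as designed, and 5.2 has no analysis set or post-rescue rule, so treatment failures can leave the comparison or be masked by rescue

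*Combined protocol and SAP*

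**What the plan says.** - **Allocation and replacement (5.1).** On enrolment the subject is "assigned a number that will both assign the subject to one of the arms". Up to 500 may consent so that 210 complete each group, and then: "Therefore, we will be replacing subjects that do not complete the study as designed". No section says what completing as designed means.
- **Blinding (3.2.1).** "The study is not blinded to the subject or investigator".
- **Exit (4.3).** "all subjects retain the ability to be excluded from the study and undergo the procedure of their choice at any point".
- **Failure and rescue (3.2.3).** If the orthostatic headache score is unchanged 30 minutes after a third SPGB, "the procedure will be considered a failure and conservative measures or an EBP will be offered to the patient". Later, "If patients in any group on telephone interview note dissatisfaction with the alleviation of the symptoms or if the symptoms return", the patient may choose an EBP, an SPGB or medical management.
- **Follow-up (3.2.3).** "In all cases, the same symptoms will be assessed at 24 and 48 hours post-procedure in the manner noted above".
- **Analysis (5.2).** The section names the Mann–Whitney U test, Student's t-test and a 0.05 significance level. It has no analysis set, missing-data rule, rule for scores after rescue, or test against the margin.
- **Data sheet (3.1.6).** There is no field for a rescue procedure or a crossover.

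**The concern.** The arm is fixed before replacement applies, and both patient and investigator know it. Two ways of handling a treatment failure are then open.

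**Route A, replacement.** A patient without relief leaves under 4.3, counts as not having completed, and is replaced. The comparison becomes one of completers.

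**Route B, rescue.** The patient stays, has an EBP, and the later score is analysed under SPGB. For the 24-hour score the documented path is mainly the third unsuccessful SPGB, which exists in one arm only. Rescue prompted by the 24-hour call can occur in either arm and can affect only the 48-hour score. Crediting such a score to SPGB does not fit the planning rate in 3.6: its 68% comes from the pilot described in Section 2, where it is the share of patients spared an EBP.

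In a non-inferiority trial, anything that shrinks a true difference favours the claim under test. Two analysts could also build different data sets from the same trial and both be following the plan.

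**Working it through.** **Inputs.** From 3.6 and Table 9: EBP success 0.84, SPGB success 0.68, margin 0.33, one-sided 0.05, power 0.90. Assumed, because the documents do not give them: 1:1 allocation, the share f of failures replaced, the share u of failures rescued before scoring, and the rescue success r.

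**The plan's own figure.** (1.645 + 1.282)² × (0.84×0.16 + 0.68×0.32) / (0.16 − 0.33)² = 104.3, so 105 per arm and 210 in total. Section 5.1 uses 210 per group. Both sizes are shown below, and that mismatch is a separate point to reconcile.

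**Error at the margin.** The chance of declaring non-inferiority is P = Φ((0.33 − gap)/SE − 1.645), with SE = √[(p_E(1−p_E) + p_S(1−p_S))/n]. With true success 0.84 v 0.51 the gap is 0.33 and P = 5.0% at either size.

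**Route A.** If a share f of failures is replaced, success among completers is p/(1 − f(1−p)).

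| Failures replaced | EBP | SPGB | Gap | P, 105/arm | P, 210/arm |
|---|---|---|---|---|---|
| none | 0.840 | 0.510 | 0.330 | 5.0% | 5.0% |
| 2%, both arms | 0.843 | 0.515 | 0.328 | 5.4% | 5.6% |
| 5%, both arms | 0.847 | 0.523 | 0.324 | 6.1% | 6.6% |
| 10%, both arms | 0.854 | 0.536 | 0.317 | 7.6% | 8.9% |
| 25%, both arms | 0.875 | 0.581 | 0.294 | 15.4% | 22.3% |
| 10%, SPGB only | 0.840 | 0.536 | 0.304 | 11.3% | 15.2% |
| 25%, SPGB only | 0.840 | 0.581 | 0.259 | 32.4% | 51.3% |
| 10% SPGB, 25% EBP | 0.875 | 0.536 | 0.339 | 3.6% | 3.2% |
| 25%, EBP only | 0.875 | 0.510 | 0.365 | 1.2% | 0.6% |

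**When the gap shrinks.** Let a and b be the shares of the EBP and SPGB arms removed as failures. For small shares the gap is unchanged when 0.84a = 0.51b. With equal arms, SPGB must then supply more than 0.84/(0.84 + 0.51) = 62% of the replaced failures before the gap shrinks. Exactly, replacing 10% of SPGB failures (4.9% of that arm) is offset by 19% of EBP failures (3.0% of that arm), and 4.9/7.9 is again 62%. In the table's 10% v 25% row SPGB supplies 4.9/(4.9 + 4.0) = 55%, a majority, yet the gap widens.

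The same-share result is also conditional. It holds for every f only if the two success rates sum to at least 1. Here they sum to 1.52 as planned and 1.35 at the margin. At 0.40 v 0.20 with f = 0.25 the gap would go from 0.200 to 0.221.

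**Route B.** Apparent success is p + (1−p)·u·r. With u from 0.10 to 0.25 and r from 0.50 to 0.84, equal rescue in both arms gives P of 8.5% to 33.0% at 105 per arm and 10.5% to 52.3% at 210. With u from 0.02 to 0.05 it is 5.6% to 7.9% and 5.8% to 9.4%. Given the timing above, the both-arm case fits a 48-hour score, not a 24-hour one.

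**The consent ceiling.** At 0.84 v 0.51, reaching 210 completers per arm with 10% to 25% of failures replaced needs 434 to 458 randomised, n/(1 − f(1−p)) summed over arms. That is below 500, so the ceiling does not prevent Route A.

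**The case against.** **Failures need not be replaced.** A patient declared a failure under 3.2.3 is still scored at 24 and 48 hours, so can be read as having completed. Section 4.3 offers exit as protection against distress from randomisation and does not mention treatment failure. This stands: a reader might infer that the plan replaces treatment failures, but the text only permits it. The milder reading leads to Route B, for which there is also no rule.

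**Some exclusions are harmless.** Section 7.1 excludes patients for a positive pregnancy test or a low platelet count found after enrolment. These are baseline reasons and would not bias the comparison. The ceiling of 500 counts consents, so some replacement may precede randomisation. This stands too.

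**Direction.** A reader might infer that the bias always favours SPGB, or does so whenever most replaced failures come from SPGB. Neither follows, as the 62% threshold shows.

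**The error rates belong to a test that 5.2 does not contain.** Correct. They use the margin criterion of 3.6 with assumed rates, and no effect on the Mann–Whitney comparison has been calculated.

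**Replacement itself does not bias.** Also correct. The harm comes from leaving the replaced subject out of the analysis, so enrolling further patients need not be banned.

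**Conclusion.** The gap is real and should be fixed. Replacement after allocation is a stated rule with an undefined trigger, and nothing in 5.2 keeps a replaced or rescued patient's outcome in the comparison as a result of the assigned treatment.

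At this trial's rates the difference moves toward non-inferiority if the same share of failures is replaced in each arm or if only SPGB failures are. Exits unrelated to outcome do not move it, and replacing relatively more EBP failures widens it. The size is unknown: for same-share replacement the illustrative error runs from barely above 5% (low exit rates) to 22.3% (25% of failures, 210 per arm).

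The documents do not support a claim that the trial is biased toward SPGB. They support a claim that the plan leaves that bias uncontrolled. Because direction and size depend on rates that are not given, this is a should-fix and not a fatal flaw.

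**What to change.** - **5.1.** State that no randomised subject is dropped from the analysis because of replacement. Additional enrolment may continue, and replacement before randomisation is fine.
- **5.2, analysis sets.** Include a comparison of all randomised subjects in their assigned arm, alongside a per-protocol analysis. Define what completing as designed means for that set.
- **5.2, scores after rescue.** Pre-specify one rule, the same in both arms, under which a score taken after a rescue procedure for persistent or returning headache is not credited to the assigned treatment. Examples are counting it as failure for a success endpoint, or worst rank for the visual analogue scores. Other rules are acceptable if fixed in advance. Report observed scores as a sensitivity analysis.
- **What is not automatically a failure.** The repeat SPGBs in 3.2.3 and crossovers by preference. Scoring preference crossovers as failures can itself mislead: if 5% of the EBP arm chose SPGB by preference and were counted as EBP failures, the illustrative error would be 16.5% at 105 per arm.
- **3.1.6.** Add the date, type and reason of any rescue or crossover to the data sheet.

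The cost is wording in two sections and an addition to the data sheet. SPGB success may look slightly less favourable, and subjects who leave will have missing outcomes that need a stated rule. With complete outcomes, and failed or rescued patients counted as failures, 105 per arm keeps 90.2% power at the planning rates and a 5.0% error at the margin. Patient care is unchanged.
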